11.12 Subject Insurance and Indemnity

The sponsor will provide insurance for any subjects participating in the study in accordance with all applicable laws and regulations.

6.11.2 Analysis of secondary efficacy endpoints.....	16

[figure not shown]

Statistical Analysis Plan

6.12	Safety Analysis.....	18
6.12.1	Extent or Exposure.....	18
6.12.2	Adverse Events.....	18
6.12.3	Laboratory Tests	19
6.12.4	Vital Signs	19
6.12.5	Physical Measurement (Body Weight)	19
7.	Plan for Revision of Analysis Method	19
8.	TLF shell	19
9.	Roles and Responsibilities	22
10.	Applied SOPs	22
11.	Applied SOP SDs	22

1. Study Design

This is a multicenter, open label, single arm, for therapeutic use, study.

Prior to the study initiation, approval from IRB of each study site as well as written contract is required. Prior to the study participation, patients should receive sufficient explanation about the study and provide written consent regarding the access to and use of personal and medical information. After the consent process, subjects who meet all of the inclusion criteria and none of the exclusion criteria will receive the investigational product (Fycompa film-coated tablet). Information on baseline seizure count (frequency) will be collected retrospectively by the subject or guardian. This study consists of titration period (12 weeks) and maintenance period (24 weeks).

[Titration period (12 weeks)]

Subjects will initiate perampanel at 2 mg/day, which can be increased up to 12 mg by increments of 2 mg no more frequently than at 2-week interval according to the investigator's judgment. The dose can be maintained or reduced based on the subject's clinical response and tolerability according to the investigator's judgment. Subjects who cannot tolerate 4 mg/day will be withdrawn from the study. Subjects who are taking concomitant drugs that shorten the half-life of perampanel (phenytoin, carbamazepine, oxcarbazepine, etc.) will titrate the dose by increments of 2 mg/day no more frequently than at 1-week interval. Adjusting the type or dose of concomitant anti-epileptic drug is not allowed during this period.

[Maintenance period (24 weeks)]

Throughout the maintenance period, subjects will maintain the dose administered at the end of the titration period. However, the dose can be increased to maximum 12 mg/day or reduced to minimum 4 mg/day based on the subject's clinical response and tolerability according to the

CONFIDENTIAL

investigator's judgment. Subjects who reduce the dose during the maintenance period can increase the dose once tolerability is improved. Subjects who cannot tolerate 4 mg/day will be withdrawn from the study. Adjusting the type or dose of concomitant anti-epileptic drug is not allowed during this period.

In case of withdrawal, the dose will be tapered down and follow-up visit will take place 4 weeks after the last dose.

Subjects will visit the site for Visit 1 (Week 0), Visit 2 (Week 6), Visit 3 (Week 12), Visit 4 (Week 24) and Visit 5 (Week 36).

2. Study Objectives

2.1. Primary Objective

To evaluate the efficacy of perampanel added to monotherapy in patients with partial onset seizures with or without secondary generalization as measured by 50% responder rate

2.2. Secondary objectives

- 1) To evaluate the safety of perampanel added to monotherapy in patients with partial onset seizures with or without secondary generalization
- 2) To evaluate efficacy of perampanel added to monotherapy in patients with secondary generalized tonic clonic seizure

3. Justification of Sample Size

This study determines the efficacy and safety of perampanel as add-on therapy in patients with partial onset seizure. Primary efficacy endpoint is the 50% responder rate for partial onset seizure with or without secondary generalization. According to Bernhard J. Steinhoff et al.³⁴, the 50% responder rate was 35.3% in the test group and 19.3% in the control group. To ensure 90% power at two-sided significance level of 5%, 94 subjects are required. Considering 10% drop-out rate, a total of 105 subjects are required.

$$n = \frac{(Z_{\alpha/2} + Z_{\beta})^2 [p_T(1 - p_T)]}{(p_T - p_R)^2}$$

CONFIDENTIAL

$$= \frac{(1.96 + 1.282)^2 [0.353(1 - 0.353)]}{(0.353 - 0.193)^2}$$
$$= 93.77 \approx 94$$

$Z_{\alpha/2}$: Type I error (0.05/2)

Z_{β} : Type II error (0.1)

p_T : 50% responder rate in the test group

p_R : Reference value

4. Efficacy and Safety Endpoints

4.1 Efficacy Endpoints

4.1.1 Primary Efficacy Endpoint

50% responder rate for partial onset seizures with or without secondary generalization: the proportion of subjects achieving at least 50% reduction in the frequency of partial onset seizures with or without secondary generalization during the maintenance period compared to baseline

4.1.2 Secondary Efficacy Endpoints

- 1) 75% responder rate for partial onset seizures with or without secondary generalization
 - 2) 100% responder (seizure free) rate for partial onset seizures with or without secondary generalization
 - 3) Percent change from baseline in the frequency of partial onset seizures with or without secondary generalization during the titration period and maintenance period
 - 4) 50% responder rate for secondary generalized tonic-clonic seizure
 - 5) 75% responder rate for secondary generalized tonic-clonic seizure
 - 6) 100% responder (seizure free) rate for secondary generalized tonic-clonic seizure
 - 7) Percent change from baseline in the frequency of secondary generalized tonic-clonic seizure during the titration period and maintenance period
- * Secondary generalized tonic-clonic seizure is collected as 'complex partial onset seizure with secondary generalization'

4.2 Safety Endpoints

- 1) Adverse events
- 2) Laboratory tests
- 3) Vital signs
- 4) Physical measurements

5. Analysis Sets

5.1 Efficacy Analysis Set

Efficacy is analyzed primarily in the Full Analysis Set (FAS), and secondarily in the Per-Protocol Set (PPS). Safety is analyzed in the Safety Analysis Set.

- FAS: subjects who received at least one dose of investigational product and were assessed for primary efficacy at least once during the maintenance period (Week 12 - 5 days ~ Week 36 + 7 days).
- PPS: subjects in FAS who completed the study per protocol without major violation. Subjects who meet any of the following conditions are excluded from PPS.
 - 1) Deviation from selection criteria
 - 2) Use of prohibited concomitant medication or therapy
 - 3) Withdrawal
 - 4) Deviation from treatment compliance
 - 5) Other deviation considered as major protocol violation

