6.3 Handling of Withdrawal and Missing Data

All evaluation data will be analyzed as is without imputation for missing data.

In the analysis of duration of disease, missing month of the date of epilepsy diagnosis will be substituted with June and missing day will be substituted with 15. If the year is missing, the date of epilepsy diagnosis will be handled as missing data. If imputation results in negative duration of disease, the duration of disease will be 0.

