6.7 Sensitivity Analysis

Sensitivity analysis is not planned.

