6.8.4 Analysis Sets

Number of subjects included in the Safety Analysis Set, FAS, and PPS is presented. Reason for exclusion from the data set is presented using frequency and percentage.

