6.11 Efficacy Analysis

In the efficacy analyses, seizure frequency is calculated as follows.

- Seizure frequency during the screening period = (number of seizure / (date of Visit 1 – date of 8 weeks prior to Visit 1)) x 28
- Seizure frequency during the titration period = (number of seizure / (date of end of Visit 3 or date of withdrawal during the titration period – date of start of Visit 2)) x 28
- Seizure frequency during the maintenance period = (number of seizure / (date of end of Visit 5 or date of withdrawal during the maintenance period – date of start of Visit 4)) x 28

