6.12.5 Physical Measurement (Body Weight)

Results at baseline (Visit 1), Week 36 (Visit 5), end-of-study visit, and follow-up as well as the change from baseline to each timepoint post-treatment are presented using descriptive statistics (number of subjects, mean, standard deviation, median, minimum, and maximum).

7. Plan for Revision of Analysis Method

Revision of analysis method is not planned.

8. TLF shell

List of Tables

Table	Table Description
-------	-------------------

Number	
s1	14.1.1 Subject Disposition - All Enrolled Subject
s2	14.1.2 Subject Disposition by Study Site - All Enrolled Subject
s3	14.1.3 Major Protocol Deviations - All Enrolled Subject
s4	14.1.4 Analysis Sets - All Enrolled Subject
b1	14.1.5 Demographic Characteristics - Full Analysis Set
b2	14.1.6 Baseline Disease Characteristics - Full Analysis Set
b3	14.1.7 Past Medical History - Full Analysis Set
b4	14.1.8 Current Medical History - Full Analysis Set
b5	14.1.9 Previous Medications - Full Analysis Set
b6	14.1.10 Concomitant Medications - Full Analysis Set
b7	14.1.11 Previous Medications (anti-epileptic drugs) - Full Analysis Set
b8	14.1.12 Concomitant Medications (anti-epileptic drugs) - Full Analysis Set
b9	14.1.13 Concomitant Non-Pharmacological Therapy - Full Analysis Set
e1_1	14.2.2.1 50% Responder Rate for Partial Onset Seizures with or without Secondary Generalization - Full Analysis Set
e1_2	14.2.2.2 50% Responder Rate for Partial Onset Seizures with or without Secondary Generalization - Per Protocol Set
e2_1	14.2.3.1 75% Responder and 100% Responder (Seizure-Free) Rate for Partial Onset Seizures with or without Secondary Generalization - Full Analysis Set
e2_2	14.2.3.2 75% Responder and 100% Responder (Seizure-Free) Rate for Partial Onset Seizures with or without Secondary Generalization - Per Protocol Set
e3_1	14.2.4.1 Percent Change in the Frequency of Partial Onset Seizures with or without Secondary Generalization during the Titration Period and Maintenance Period compared to Screening Period - Full Analysis Set
e3_2	14.2.4.2 Percent Change in the Frequency of Partial Onset Seizures with or without Secondary Generalization during the Titration Period and Maintenance Period compared to Screening Period - Per Protocol Set
e4_1	14.2.5.1 - 50% Responder, 75% Responder, and 100% Responder (Seizure-Free) Rate for Secondary Generalized Tonic-Clonic Seizure - Full Analysis Set

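### No planned responder rate counts dosed subjects who leave during titration, because the FAS requires a maintenance-window assessment and no sensitivity analysis is planned

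*SAP*

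**What the plan says.** SAP 5.1 requires, for the FAS, at least one dose and that the subject be "assessed for primary efficacy at least once during the maintenance period (Week 12 - 5 days ~ Week 36 + 7 days". The supportive set is narrower: "PPS: subjects in FAS who completed the study per protocol without major violation", with withdrawal listed as a reason for exclusion.

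SAP 1 foresees exits during titration: "Subjects who cannot tolerate 4 mg/day will be withdrawn from the study". Protocol 9.5.5 says removed subjects may not be replaced.

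On missing data, SAP 6.3 states "All evaluation data will be analyzed as is without imputation for missing data", and SAP 6.7 states "Sensitivity analysis is not planned".

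The primary table listed in SAP 8 is the "50% Responder Rate for Partial Onset Seizures with or without Secondary Generalization - Full Analysis Set". Its companion, and every other efficacy table (e1 to e5), is on the FAS or PPS.

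For the analysis sets, SAP 6.8.4 adds: "Reason for exclusion from the data set is presented using frequency and percentage". SAP 6.8.1 tabulates discontinuations by reason.

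In SAP 6.11 the maintenance seizure frequency ends at Visit 5 or at withdrawal during maintenance, and its interval begins at the "date of start of Visit 4". That date is not defined.

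**The concern.** The primary result of this single-arm study is one proportion with its confidence interval, so the denominator matters. Under the SAP, subjects who took the drug and left in titration, including those who could not tolerate the dose named in SAP 1, are in neither the numerator nor the denominator. The result describes those who reached maintenance and is silent on what happened to everyone who started treatment.

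If early leavers would have responded less often than those who stayed, the reported rate is higher than the rate in all treated subjects. There is no comparator arm in which such selection could be seen. Protocol 7.3.3.3 also describes the source of the planning rates (35.3% and 19.3%) as an intention-to-treat analysis, so a rate restricted to subjects reaching maintenance is a less like-for-like companion to those figures.

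A related wording gap makes the FAS itself uncertain at its edge. The FAS window opens 5 days before Week 12, which can include Visit 3, while the maintenance interval in SAP 6.11 starts from an undefined date tied to Visit 4 (Week 24). The SAP does not say whether a subject last seen at Visit 3 is in the denominator or, if so, how that subject is classified.

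**Working it through.** **1. The plan's own figure.** Protocol 9.7.2 and SAP 3 use p_T = 0.353, p_R = 0.193, and z-values 1.96 and 1.282:

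n = (1.96 + 1.282)² × 0.353 × 0.647 / (0.353 − 0.193)² = 93.77, rounded up to 94.

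94 / 0.90 = 104.4, rounded up to 105. Both totals reproduce. The 10% allowance is for drop-out overall and is not split by period.

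**2. Is a titration leaver counted anywhere?**

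- FAS: needs an assessment in the maintenance window, so no.
- PPS: a subset of the FAS that excludes withdrawals, so no.
- Missing-data rule: no imputation and no non-responder rule, so no.
- Sensitivity analysis: none planned.
- Seizure-frequency formula: the maintenance formula has no term for withdrawal in titration.
- Titration percent change (tables e3 and e5): also on the FAS and PPS only, so these subjects' titration diaries enter no efficacy table.

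Subjects who withdraw during maintenance are different. SAP 6.11 provides an end date for them and they can remain in the FAS. The gap concerns titration leavers only.

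**3. Size of the effect.** Let L be the number of 105 dosed subjects who leave in titration, r their response rate, and 35.3% the FAS rate.

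All-dosed rate = [(105 − L) × 0.353 + L × r] / 105

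Gap = (L/105) × (0.353 − r)

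L is an assumption, since the documents do not give it. L = 11 places the whole planned drop-out in titration, so it is an upper case for the 10% figure.

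| L of 105 | All-dosed rate, r = 0 | Gap (points) | All-dosed rate, r = 19.3% | Gap (points) |
|---|---|---|---|---|
| 3 | 34.3% | 1.0 | 34.8% | 0.5 |
| 5 | 33.6% | 1.7 | 34.5% | 0.8 |
| 8 | 32.6% | 2.7 | 34.1% | 1.2 |
| 11 | 31.6% | 3.7 | 33.6% | 1.7 |

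For example, with L = 11 and r = 0: 94 × 0.353 / 105 = 33.18 / 105 = 31.6%. With r = 35.3% the gap is zero for every L.

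**4. In whole counts, with exact (Clopper-Pearson) 95% intervals** and leavers as non-responders:

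- 5 leavers: 35/100 = 35.0% (25.7 to 45.2) on the FAS, against 35/105 = 33.3% (24.4 to 43.2) over all dosed.
- 11 leavers: 33/94 = 35.1% (25.5 to 45.6) on the FAS, against 33/105 = 31.4% (22.7 to 41.2) over all dosed.

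The FAS half-widths are 9.7 and 10.1 points, so the shift is well inside sampling error. The 19.3% reference is a planning value and not a success rule, so no probability of clearing it is claimed.

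**The case against.** The strongest case against is that this is little more than a preference. The endpoint is defined over the maintenance period, so asking for maintenance data follows from it. The sample size openly takes drop-outs out of the denominator, and all analyses are descriptive. The counts needed are already planned: the FAS responder count divided by the number dosed gives the all-dosed rate under a non-responder rule. The effect is small and rests on an assumed number of leavers. Withdrawal for intolerance is not evidence of non-response, so an upward bias is not shown.

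Much of this stands. The protocol's FAS (9.7.1.2) also needs a postdose primary efficacy measurement, so no departure from the protocol is alleged. The direction is conditional on leavers responding less often; only the non-responder rule guarantees a lower figure. A reader could approximate the rate by hand, although no interval would be prespecified and the Visit 3 case would remain open. A descriptive purpose does not remove the point, because the estimate and its interval are then the whole result.

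It can also be argued that some titration leavers fall inside the FAS window. Diaries are dispensed at discontinuation and reviewed at follow-up, nominally 4 weeks after the last dose. The window opens at Day 84 − 5 = 79, so a last dose at about Day 79 − 28 = 51 or later could give a review after it opens. That reading is strained: such a subject never entered maintenance, and SAP 6.11 gives no maintenance interval from which to classify them.

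**Conclusion.** The concern holds. As written, the SAP yields responder rates conditional on reaching maintenance and prespecifies no rate or interval over all dosed subjects. Over the assumed range of 3 to 11 leavers among 105, with a FAS rate of 35.3%, the reported rate would exceed the all-dosed rate by 1.0 to 3.7 points if leavers do not respond, and by 0.5 to 1.7 points if they respond at 19.3%. There is no difference if they respond as stayers do.

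This is worth fixing because the check is cheap and the design has no other way to show the selection. It does not invalidate the primary analysis or the sample size. The unclear status of a subject last seen at Visit 3 is a separate drafting gap that does not depend on these assumptions.

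**What to change.** Keep the FAS analysis as primary, as Protocol 9.7.1.5 requires. Then change the SAP as follows:

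- **SAP 6.7:** replace the statement that none is planned with a sensitivity analysis giving 50%, 75% and 100% responder rates over all dosed subjects, with exact 95% intervals. Subjects with no evaluable maintenance data count as non-responders. Define evaluable as having a maintenance seizure frequency that can be calculated under SAP 6.11.
- **SAP 8:** add the corresponding table, labelled as a sensitivity analysis.
- **SAP 6.11 and 5.1:** define the start date of the maintenance interval, reconcile it with the FAS window, and state whether a subject last seen at Visit 3 is in the FAS and how that subject is counted.

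The cost is some SAP wording and one table, with no new data. The downside is a second, somewhat lower rate (about 1 to 4 points over the assumed range), which can understate the effect if some leavers had improved. The label should make that clear.

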5.2 Safety Analysis Set

Safety is analyzed in the Safety Analysis Set.

- Safety Analysis Set: subjects who received at least one dose of investigational product and were assessed for safety at least once.

6. Statistical Analysis Method

6.1 Analysis Program

Statistical analysis will use SAS® Version 9.4 (SAS Institute, Cary, NC, USA) or subsequent version.

6.2 General Principles of Result Analysis

All analyses will be descriptive. Continuous variables will be presented using descriptive statistics (number of subjects, mean, standard deviation, median, minimum and maximum), while categorical variables will be presented using frequency and percentage. In addition, with regard to efficacy, 95% confidence interval (t-distribution) for the mean will be presented for continuous variables, while 95% exact confidence interval will be presented for categorical variables. Values with a decimal point, such as mean, standard deviation, and percentage, will be rounded to two decimal places.

6.3 Handling of Withdrawal and Missing Data

All evaluation data will be analyzed as is without imputation for missing data.

In the analysis of duration of disease, missing month of the date of epilepsy diagnosis will be substituted with June and missing day will be substituted with 15. If the year is missing, the date of epilepsy diagnosis will be handled as missing data. If imputation results in negative duration of disease, the duration of disease will be 0.

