9.5.5 Completion/Discontinuation of Subjects

A subject may elect to discontinue the study at any time for any reason. All subjects who discontinue the study are to complete the study's early discontinuation procedures indicated in the Schedule of Procedures/Assessments (Table 2).

The investigator will promptly explain to the subject involved that the study will be discontinued for that subject and provide appropriate medical treatment and other necessary measures for the subject. A subject who has ceased to return for visits will be followed up by mail, phone, or other means to gather information such as the reason for failure to return, the status of treatment compliance, the presence or absence of AEs, and clinical courses of signs and symptoms.

Subjects who discontinue early from the study will be discontinued for 1 of these primary reasons: AE(s), lost to follow-up, subject choice, inadequate therapeutic effect, progression of disease, withdrawal of consent, pregnancy, study terminated by sponsor, or other. In addition to the primary reason, the subject may indicate 1 or more secondary reason(s) for discontinuation. Study disposition information will be collected on the Subject Disposition CRF.

A subject removed from the study for any reason may not be replaced.

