9.7.1.1 Study Endpoints

9.7.1.1.1 PRIMARY ENDPOINT

50% responder rate in total seizures: 50% responders are defined as subjects who have at least 50% reduction in total seizure frequency during the Maintenance Period relative to the Baseline.

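### A subject who stops perampanel early in maintenance can count as a 50% responder in the primary FAS rate on a very short record, and no planned FAS table shows the effect

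*SAP*

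**What the plan says.** Protocol 9.7.1.1.1 defines the primary endpoint: "50% responders are defined as subjects who have at least 50% reduction in total seizure frequency during the Maintenance Period relative to the Baseline". It does not say how a subject who leaves during maintenance is classified, and neither do SAP 4.1.1 and 6.11.1.

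Four SAP sections together decide what happens to such a subject:

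- SAP 5.1 admits to the FAS anyone dosed who was "assessed for primary efficacy at least once during the maintenance period (Week 12 - 5 days ~ Week 36 + 7 days"). One assessment is enough.
- SAP 6.11 divides the seizure count by the interval "date of end of Visit 5 or date of withdrawal during the maintenance period – date of start of Visit 4" and multiplies by 28. No minimum interval is set.
- SAP 6.3, the section on withdrawal and missing data, says "All evaluation data will be analyzed as is without imputation for missing data".
- SAP 6.7 says "Sensitivity analysis is not planned".

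Withdrawal is a condition for exclusion from the PPS (SAP 5.1). Protocol 9.5.5 foresees discontinuation for adverse events and for "inadequate therapeutic effect, progression of disease, withdrawal of consent, pregnancy", among other reasons. Protocol 9.5.2.2.2 has the diary returned and reviewed at the discontinuation visit, so a short maintenance record can reach the analysis.

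**The concern.** Scaling to 28 days puts every record on the same unit but does not make the 50% threshold equally hard to meet at every length. At the entry minimum, a maintenance record shorter than 56 days is a response exactly when it contains no seizure. That is a likely result over one or two weeks even if the seizure rate has not moved. A subject who could not stay on the drug then adds to the headline rate on the same footing as a 24-week completer.

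The study has one arm, so the responder rate and its exact confidence interval are its main result, and no control arm shares the distortion. The PPS does not fill the gap: it takes withdrawals out of the denominator. No planned table gives a rate in which stopping the drug counts against the drug, or shows how many responders rest on short records.

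**Working it through.** **The plan's own figure.** n = (1.96 + 1.282)² × 0.353 × 0.647 / (0.353 − 0.193)² = 93.77, so 94; 94 / 0.90 = 104.4, so 105. The sample size reproduces and is not affected by this point.

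**Inputs.** Baseline of 56 days (Protocol 9.5.1.2); at least 2 baseline seizures (Protocol 9.3.1, criterion 4); maintenance of 168 days for a completer (Protocol 9.1); frequency per 28 days (Protocol 9.7.1.5). Assumptions: Poisson counts, a true rate equal to the observed baseline rate, and a maintenance interval that starts at Week 12.

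**Threshold.** With X baseline seizures and c seizures in T maintenance days, response requires 28c/T ≤ 0.5 × 28X/56, that is c ≤ 0.5·X·T/56. For X = 2 this is c ≤ T/56, so zero seizures for any T below 56.

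**Chance of a false response**, P(Poisson(XT/56) ≤ ⌊0.5·XT/56⌋):

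| Baseline | 7 days | 14 days | 28 days | 168 days |
|---|---|---|---|---|
| X = 2 | e^−0.25 = 77.9% | e^−0.5 = 60.7% | e^−1 = 36.8% | P(Poisson(6) ≤ 3) = 15.1% |
| X = 4 | 60.7% | 36.8% | 40.6% | P(Poisson(12) ≤ 6) = 4.6% |

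At X = 2 the ratios to a completer are 5.2, 4.0 and 2.4.

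**Effect on the FAS rate.** The documents give no number or timing of maintenance withdrawals; 10 of 94 is assumed. Excess = 10 × (mean chance over withdrawal times − full-length chance) / 94.

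- Leaving uniformly over days 1 to 56: the means are 0.429, 0.378 and 0.321 for X = 2, 3 and 4, against 0.151, 0.055 and 0.046. The excess is 3.0, 3.4 and 2.9 points.
- Leaving uniformly over days 1 to 168: the means are 0.259, 0.199 and 0.160. The excess is 1.2, 1.5 and 1.2 points.

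**How far this depends on the assumptions.** At 7 and 14 days, the ratio to a completer is:

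- 2.4 and 1.9 with regression to the mean (true rate 1 per 28 days, selected on at least 2 seizures);
- 2.2 and 1.7 with negative binomial counts (X = 2, dispersion 0.5 assumed);
- 2.1 and 1.8 with a true 30% reduction (X = 2);
- 1.4 and 1.2 with a true 50% reduction (X = 2).

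The chance is not monotone in time. At X = 4 it rises from 36.8% at 14 days to 40.6% at 28. At X = 2 and 55 days it is 14.0%, just below the completer's 15.1%.

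The sign can also reverse. With a true 60% reduction and X = 2, the chance of being scored a responder is 67% at 28 days and 55% at 42, against 78% for a completer. In the scenario of 10 leaving within 56 days, the excess at a true 50% reduction is about −0.1 points for X = 2 and X = 4 (+1.1 for X = 3). At a true 60% reduction it is −0.9, −0.1 and −1.2 points for X = 2, 3 and 4.

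**The start of the interval.** SAP 6.11 starts the maintenance denominator at the start of Visit 4, and Visit 4 is Week 24, Day 168. Read literally, a subject who withdraws 14 days into maintenance (Day 98) has a denominator of 98 − 168 = −70 days. Every withdrawal between Weeks 12 and 24 would then have a zero or negative denominator and no valid rate. The titration formula starts at Visit 2 in the same way, although titration begins at Week 0. This suggests that each visit label stands for the diary period ending at that visit, but the SAP does not say so.

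**The case against.** SAP 6.11 is a rule: it ends the rate at the "date of withdrawal during the maintenance period". A reader might infer that the plan has no rule at all for these subjects, and that would be wrong. What is missing is narrower: a responder status for those who stop, a minimum record length, and any check on the result.

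A reader might also infer that the bias always favours the drug. The calculations do not support this. The excess is clear when nothing has changed. It is near zero for baselines of 2 and 4 at a true 50% reduction, and turns negative at 60%. Short records misclassify in both directions.

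The size is uncertain. The plan already allows 10% drop-out to keep 94 for the primary analysis, so a further 10 withdrawals within the 94 is an assumption. Protocol 7.3.3.4 reports that in the phase III extension study adverse events were most frequent during titration. Subjects lost to follow-up after Week 12 will usually return no maintenance diary, so there may be nothing to score.

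The analysis is descriptive and no hypothesis is tested. One subject is worth 1.1 points and can carry the exact lower limit across the 19.3% reference value (26/94 gives 18.9%, 27/94 gives 19.9%), but only at that margin. At about the planned rate (33/94, lower limit 25.5%), seven responders would have to be reclassified.

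These points limit the size and rule out a claim of one-way bias. They do not remove the gap: a descriptive rate still needs a defined outcome for every FAS member, and the PPS does not supply one.

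**Conclusion.** The point holds at modest severity. The primary FAS rate can include responders whose maintenance record is a few days or weeks long, and nothing planned shows how many. With Poisson counts, no true change and an interval starting at Week 12, such a subject at the entry minimum is about 2.4 to 5.2 times as likely as a completer to be scored a responder at 1 to 4 weeks. The ratio is smaller with regression to the mean, over-dispersion or a true effect. If 10 of 94 withdrew in maintenance, the no-effect excess is about 1 to 3 points; with a true reduction of about 50% or more it can vanish or reverse.

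The documents do not support the stronger inference that the headline rate is necessarily inflated. They support saying that its dependence on early withdrawals is hidden. If the interval in SAP 6.11 really starts at Week 24, the problem changes form: withdrawals between Weeks 12 and 24 have no valid rate. Either reading needs text in the SAP.

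**What to change.** - **SAP 6.3, 6.11.1 and Table 14.2.2.1:** add a pre-specified FAS 50% responder rate with exact 95% CI in which a subject who stops perampanel before Week 36 of the study counts as a non-responder. As a minimum, apply this to subjects with fewer than 56 maintenance days, the length of the baseline.
- **Same table:** keep the observed-data rate beside it, and show responders by maintenance time (under 56 days, 56 days to before Week 36, completed).
- **SAP 6.7:** amend to name this analysis.
- **SAP 6.11:** state that the maintenance interval starts at the Week 12 visit.

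The cost is a few sentences and some extra table rows, from data already collected. The added rate will be somewhat lower and is conservative, because it also counts as failures genuine responders who leave for unrelated reasons. Showing the observed-data rate alongside limits that drawback.
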